### 5.3.2 Discontinuation of Study Intervention

Immunosuppression withdrawal will be discontinued for a participant if he or she experiences any of the following:

- A second episode of mild rejection not requiring treatment.
- Any episode of rejection (mild, moderate, or severe) requiring treatment.
- Chronic rejection.
- Abnormal LFTs in the absence of biopsy-proven rejection that do not substantially improve (see section 5.5.2) within the maximum interval specified in section 5.3.1, Interruption of Study Intervention.

Such participants will be considered to have failed immunosuppression withdrawal.

Participants who fail immunosuppression withdrawal will move into the medium-intensity follow-up schedule (see Appendix 2) for 52 weeks after their LFTs have improved (see section 5.5.2) and then will be discharged from the study.

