## 6.6 FOLLOW-UP ASSESSMENTS

[figure not shown]
Frequency of visits and the number of assessments performed will depend on whether the patient is undergoing high-, medium-, or low-intensity follow-up (see Figure 3 and Appendices 1–3).

All participants who successfully withdraw from immunosuppression must complete 12 weeks of high-intensity follow-up, 104 weeks of medium-intensity follow-up, and 104 weeks of low-intensity follow-up (see Appendices 1–3). The 12 weeks of high-intensity follow-up will begin immediately after the last dose of immunosuppressant medication is taken.

All participants who remain off immunosuppression after successful completion of low- intensity follow-up will undergo 208 weeks (4 years) of Extended Follow-up as described in Appendix 4.

Participants who experience any episode of rejection after successful complete of immunosuppression withdrawal will move into the medium-intensity follow-up schedule (see Appendix 2) for 52 weeks after their LFTs have improved (see section 5.5.2). They will then be discharged from the study.

Participants who fail immunosuppression withdrawal will move into the medium-intensity follow-up schedule (see Appendix 2) for 52 weeks and then will be discharged from the study.

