3.4 Overall Study Design and Plan

This is a prospective multicenter, open-label, single-arm trial in which 20 pediatric recipients of parental living-donor liver allografts will undergo gradual withdrawal of immunosuppression with the goal of complete withdrawal. Subjects on stable immunosuppression regimens with good organ function and no evidence of acute or chronic rejection or other forms of allograft dysfunction will be enrolled. Subjects will undergo gradual withdrawal of immunosuppression and will be followed for a minimum of 4 years after completion of immunosuppression withdrawal. Immunologic and genetic profiles will be collected at multiple time points and compared between tolerant and nontolerant subjects.

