10.3 Adverse Events

All adverse events will be coded using the MedDRA dictionary, including classification by system organ class (SOC) and preferred term. The severity of adverse events (AE) will be classified using the National Cancer Institute's Common Toxicity Criteria for Adverse Events toxicity scale.

An overall summary table will be developed to report the number of events and the number and percentage of subjects having at least one event in the following categories:

- Adverse events (AEs)
- Serious Adverse Events (SAEs)
- Deaths
- AEs reported as definitely, probably, or possibly related to immunosuppression withdrawal
- AEs reported by severity

The tabulations described above will not include classifications by SOC and preferred term.

In addition, a summary table of adverse events classified by MedDRA SOC and preferred term will be provided for each of the following:

- AEs
- AEs by maximum severity
- AEs by relationship to immunosuppression withdrawal.

The summary tables will present the total number of events as well as the number and percentage of subjects experiencing the events by clinical phenotype. When reporting the number of AEs, if the same AE occurs for a subject on multiple occasions the event will be counted once for each occurrence. When reporting the number of subjects experiencing the events, a subject will only be counted once if they ever experience an event within the particular system organ class or preferred term. Percentages will be based on the number of subjects categorized in each clinical phenotype.

Separate data listings will be provided for all AE and AEs leading to treatment discontinuation/study termination ordered by subject id.

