10.4 Deaths, Serious Adverse Events, and Other Significant Adverse Events

10.4.1 Deaths and Serious Adverse Events

SAEs will be listed and summarized in the same manner described in section 10.3. Separate displays listing and summarizing death, including time to death and cause of death will also be created.

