Appendix 2. Schedule of Events: Medium-intensity Follow-up

Monthly visit	Medium-intensity Follow-up ¹¹											
	M1	M2	M3	M4	M5	M6	M7	M8	M9	M10	M11	M12
	M13	M14	M15	M16	M17	M18	M19	M20	M21	M22	M23	M24
General Assessments												
Physical examination						X						X
Vital signs						X						X
Telephone consultation	X	X	X	X	X		X	X	X	X	X	
Adverse events	X	X	X	X	X	X	X	X	X	X	X	X
Concomitant medications	X	X	X	X	X	X	X	X	X	X	X	X
Study Site and Local Laboratory Assessments												
Hematology						X						X
Comprehensive chemistry						X						X
Liver panel	X	X	X	X	X		X	X	X	X	X	
Autoantibodies						X						X
Quantitative IgG						X						X
Glomerular filtration rate (creatinine and height)	X ²											X
Hemoglobin A _{1C}	X ²											X
Central Laboratory Assessments												
Whole blood–quantitative PCR for CMV reactivation ¹²	X ¹³					X						X
Whole blood–quantitative PCR for EBV reactivation ²	X ³					X						X
Liver Biopsies												
Liver biopsies ^{14, 15}												X
Tolerance Assessments^{16,17}												
Whole blood–flow cytometry panel staining						X						X

¹¹ Subjects enter medium-intensity follow-up after completing 3 months of high-intensity follow-up or after failing immunosuppression withdrawal (see section 5.3). Subjects who have successfully completed immunosuppression withdrawal will remain in medium-intensity follow up for 24 months. Subjects who fail immunosuppression withdrawal will remain in medium-intensity follow-up for 12 months and then be discharged from the study.

¹² Will be performed *only* at visit M1 and not at visit M13.

¹³ Do not collect if last sample was collected less than 6 weeks before visit M1.

¹⁴ Additional biopsies will be performed if necessary to rule out rejection.

¹⁵ Will be performed *only* at the end of the second year (i.e., month 24) of medium-intensity follow-up for those who have successfully withdrawn. Will *not* be done for those who experienced rejection and have completed 1 year of medium-intensity follow-up.

¹⁶ If a rejection episode occurs, samples for all mechanistic assessments that are scheduled for monthly visits M12 and M24 (except for whole blood–flow cytometry panel staining) will be collected at this time.

¹⁷ Do not collect for subjects who have failed immunosuppression withdrawal.

	Medium-intensity Follow-up ¹¹											
Monthly visit	M1	M2	M3	M4	M5	M6	M7	M8	M9	M10	M11	M12
	M13	M14	M15	M16	M17	M18	M19	M20	M21	M22	M23	M24
Frozen PBMC–T-cell assays						X						X

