Appendix 3. Schedule of Events: Low-intensity Follow-up

Monthly visit	Low-intensity Follow-up ¹											
	L1	L2	L3	L4	L5	L6	L7	L8	L9	L10	L11	L12
	L13	L14	L15	L16	L17	L18	L19	L20	L21	L22	L23	L24
General Assessments												
Physical examination						X						X
Vital signs						X						X
Telephone consultation		X		X				X		X		
Adverse events		X		X		X		X		X		X
Concomitant medications		X		X		X		X		X		X
Study Site and Local Laboratory Assessments												
Hematology						X						X
Comprehensive chemistry						X						X
Liver panel		X		X				X		X		
Autoantibodies						X						X
Quantitative IgG						X						X
Glomerular filtration rate (creatinine and height)												X
Hemoglobin A _{1c}												X
Central Laboratory Assessments												
Whole blood–quantitative PCR for CMV reactivation						X						X
Whole blood–quantitative PCR for EBV reactivation						X						X
Liver Biopsies												
Liver biopsies ^{2,3}												X
Tolerance Assessments⁴												
Whole blood–flow cytometry panel staining												X
Frozen PBMC–T-cell assays												X
Liver biopsy–histology ²												X
Whole blood–gene expression profiling												X
Liver biopsy RNA–gene expression profiling ²												X
Serum–secreted cytokines												X
Serum–HLA alloantibodies												X

¹ Subjects enter low-intensity follow-up after completing medium-intensity follow-up.

² Additional biopsies will be performed if necessary to rule out rejection.

³ Will be performed at the end of the second year (i.e., monthly visit L24) of low-intensity follow-up.

⁴ If a rejection episode occurs, samples for all mechanistic assessments that are scheduled for monthly visits L12 and L24 (except for whole blood–flow cytometry panel staining) will be collected at this time.

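### SAP tables of AEs and SAEs by phenotype have no time denominator, although phenotype largely decides how long a participant is observed

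*SAP*

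**What the plan says.** SAP 10.3 plans tables with the number of events and the number and percentage of subjects affected, by clinical phenotype. The denominator is a head count: "Percentages will be based on the number of subjects categorized in each clinical phenotype". SAP 10.4.1 extends this to serious events: "SAEs will be listed and summarized in the same manner described in section 10.3". SAP 3.3 defines a tolerant subject as one successfully withdrawn for at least a year and equates this with the primary endpoint.

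Follow-up depends on that outcome:

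- **Failures.** SAP Appendix 2: "Subjects who fail immunosuppression withdrawal will remain in medium-intensity follow-up for 12 months and then be discharged from the study". For participants discontinued under Protocol 5.3.2, the period runs "for 52 weeks after their LFTs have improved (see section 5.5.2) and then will be discharged from the study".
- **Participants who stay off drug.** Under Protocol 6.6 they "must complete 12 weeks of high-intensity follow-up, 104 weeks of medium-intensity follow-up, and 104 weeks of low-intensity follow-up". SAP 3.4 says subjects are "followed for a minimum of 4 years after completion of immunosuppression withdrawal", and the SAP schedule ends with low-intensity follow-up. Protocol 6.6 now adds that those still off drug "will undergo 208 weeks (4 years) of Extended Follow-up as described in Appendix 4".

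AE collection stops at the end of participation (Protocol 8.3.1) and SAE collection 30 days later (Protocol 8.3.2).

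Graft loss or death is a proportion of those starting withdrawal, counted from initiation, with an exact 95% interval (SAP 9.2.2 item 3 and 9.3.2 item 3; Protocol 9.2.2.1). No end of observation is given.

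**The concern.** A head-count percentage compares two groups fairly only if they are watched for similar lengths of time. Here the grouping variable largely sets the watching time. At equal underlying rates, the tolerant column would collect more events simply because it is open longer.

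Immortal time works the other way. To be called tolerant, a participant must finish the taper and then stay off drug for a year. A death before that point, or a rejection before it that leads to failure or restart, can fall only in the not-tolerant column. A rejection after one year stays in the tolerant column (SAP 9.2.1). A reader cannot separate these effects from a true difference, and a real excess among failures could be hidden.

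The graft-loss/death proportion has a related gap. Participants discharged after failure or lost early remain in the denominator as event-free, with nothing to show how long they were observed. Safety of withdrawal is the first secondary objective, and both AE incidence and graft loss/death are named endpoints, so the reading of these tables matters.

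**Working it through.** **Plan's own figure.** The Clopper–Pearson method gives 9/20 = 45% (23.1–68.5%) and 4/20 = 20% (5.7–43.7%), as stated in Protocol 9.3 and SAP 3.7.

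**Inputs from the documents.** Follow-up after failure is 52 weeks. Follow-up off drug is 12 + 104 + 104 = 220 weeks, or 220 × 7 / 365.25 = 4.22 years. With the protocol extension it is 220 + 208 = 428 weeks. The SAP figure is used because AE tables by phenotype appear only in the SAP.

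**Assumptions.** The documents give no SAE rate, so rates are assumed constant, equal in both phenotypes, and for events unrelated to rejection or death. The taper is taken as 0.75 year for completers (12 monthly visits in Appendix 1 less 3 months of high-intensity follow-up), with 1.75 years (24 visits less 3 months) as the alternative. LFT recovery time, early loss and the 30-day SAE tail are ignored.

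**Observation time from the start of withdrawal (0.75-year taper).**

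- Not-tolerant, shortest: failure immediately after the start, 0 + 1.0 = 1.0 year.
- Not-tolerant, longest: rejection just before one year off drug, 0.75 + 1 + 1 = 2.75 years.
- Tolerant, shortest: rejection just after one year off drug, 0.75 + 1 + 1 = 2.75 years.
- Tolerant, longest: 0.75 + 4.22 = 4.97 years.

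**Percentage with at least one SAE**, P = 1 − exp(−rate × years):

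| Rate per person-year | Taper (years) | Not-tolerant | Tolerant |
|---|---|---|---|
| 0.05 | 0.75 | 4.9–13% | 13–22% |
| 0.1 | 0.75 | 9.5–24% | 24–39% |
| 0.2 | 0.75 | 18–42% | 42–63% |
| 0.1 | 1.75 | 9.5–31% | 31–45% |

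For the last row the times are 1.0–3.75 years and 3.75–5.97 years.

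**Break-even.** Percentages are equal when the rate ratio equals the inverse ratio of the times. With the tolerant at their maximum time and a 0.75-year taper, this is 4.97/2.75 = 1.8 to 4.97/1.0 = 5.0. A not-tolerant rate that many times higher would show no difference in the table.

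**Share of person-years supplied by the tolerant, if all complete 220 weeks.**

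- 9/20 succeed: 9 × 4.97 = 44.7, against 11 × 1.0 = 11 to 11 × 2.75 = 30.3. The share is 80% down to 60%.
- 4/20 succeed: 4 × 4.97 = 19.9, against 16 × 1.0 = 16 to 16 × 2.75 = 44. The share is 55% down to 31%.

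A whole-cohort rate therefore also depends on the success rate, which is why a split by phase is useful.

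**Graft loss/death.** With 20 participants, one event missed after discharge or loss is the difference between 0/20 (0%; 0–16.8%) and 1/20 (5%; 0.1–24.9%). The documents give no basis for estimating how likely such a miss is.

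**The case against.** The best defence is that these tables are descriptive, carry no test or decision rule, and concern 20 participants, so rates will be imprecise. Other displays carry timing:

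- Kaplan–Meier time to rejection from the start of withdrawal in all PP1 subjects (SAP 9.3.2), which covers the main risk that Protocol 1.4.2 names and does not split by phenotype;
- AE frequency tables without a phenotype split (Protocol 9.4.5);
- time to death (SAP 10.4.1), dated graft losses (SAP 10.4.3) and subject profiles (SAP 6).

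This stands as to weight: it makes the matter one of reporting. It does not remove the defect, because no AE or SAE display has a time denominator. Listings leave any rate to be devised after the data are seen, and a head-count percentage in 20 participants is also imprecise.

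Some stronger readings are tempting but are not supported:

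- A reader might infer that the phenotype of lost participants is undefined. SAP 3.3 ties phenotype to the primary endpoint and SAP 9.1.1 counts loss to follow-up as failure there, so they are not-tolerant.
- A reader might set the rule in SAP 10.1 against imputing missing safety data beside the graft-loss/death proportion. That endpoint is defined and analysed in SAP Section 9, so the contrast is weak.
- A reader might fault the Protocol's ITT sample for including people who never start withdrawal. Protocol 3.6 defines enrollment as the day withdrawal starts. The problem comes only from the screening-based definition in SAP 5, combined with the ITT analysis in SAP 9.3.2 item 3, which Table 9-1 does not list.

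**Conclusion.** The concern holds as a reporting-level point. SAP 10.3 and 10.4.1 compare phenotypes on head counts although phenotype largely sets observation time: 52 weeks after failure (from LFT improvement under Protocol 5.3.2) against up to 220 weeks off drug, or 428 with the protocol extension. The 220 weeks is a maximum, since a tolerant participant who rejects soon after one year leaves about a year later.

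Under the stated assumptions, equal rates of 0.1 per person-year would show 9.5–24% against 24–39%, and a true not-tolerant excess of 1.8 to 5.0 times could be masked. These figures rest on assumed rates and taper length and illustrate the artefact; they do not forecast the trial's results.

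It would go too far to say that the tolerant column will look worse. Rejection-related events fall mainly on the not-tolerant, so the net direction is unknown. The graft-loss/death proportion lacks a stated observation time and may understate risk over full follow-up by an amount that cannot be estimated. Nothing here touches the primary endpoint or the stopping rules.

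**What to change.** 1. In SAP 10.3 and 10.4.1, add person-years observed and events per person-year for the whole PP1 cohort and by phenotype. Split them where possible by phase: taper, off drug, and after failure or restart. State that the phenotype contrast is descriptive because tolerant status carries immortal time.
2. In SAP 9.3.2 item 3, keep the graft-loss/death proportion over all follow-up, with its exact interval, for PP1 and PP2. Beside it, report total and median observation time and the number lost or withdrawn early. A proportion at a fixed horizon that every participant is scheduled to reach may be added as a supplement. It should not replace the main figure: 52 weeks from the start of withdrawal, for instance, leaves out nearly all off-drug time (52 − 39 = 13 weeks off drug with a 0.75-year taper, none with 1.75 years).
3. Reconcile the ITT definition in SAP 5 with Protocol 3.6 and 9.1, so that an endpoint counted after initiation does not include subjects who never start withdrawal.

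The cost is an SAP amendment, with the review in SAP 14 if these count as principal features, and a few table columns. The dates needed are already collected. The downside is that rates, especially by phase, will be imprecise with 20 participants.

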10.4 Deaths, Serious Adverse Events, and Other Significant Adverse Events

10.4.1 Deaths and Serious Adverse Events

SAEs will be listed and summarized in the same manner described in section 10.3. Separate displays listing and summarizing death, including time to death and cause of death will also be created.

10.4.2 Histologic Severity of Rejection Episodes

The Banff global assessment grade indicating histologic severity of rejection episodes will be summarized for the PP1, PP2 and ITT samples by clinical phenotype. Counts and percentages will be based on the number of rejection episodes.

10.4.3 Graft Loss

Data listings will be provided for graft loss, including the date of graft loss, study day, and primary cause of graft loss.

10.4.4 Allograft Dysfunction Episodes

Data listings will be provided for allograft dysfunction episodes, including the date, final clinical diagnosis, whether follow-up biopsies were performed, date of biopsies, and whether treatment was provided for rejection.

10.4.5 Change in Renal Function, Blood Pressure, Cholesterol, and Glucose Control

Renal function is measured by creatinine and GFR. The GFR for each subject will be estimated by the Schwartz Formula:

$$\text{GFR (mL/min/1.73 m}^2\text{)} = \frac{k(\text{height})}{\text{creatinine}};$$

where $k = 0.33$ in premature infants, $k = 0.45$ in full term infants to 1 year old, $k = 0.55$ in children 1 year old up to 13 years old, $k = 0.65$ in adolescent males greater than 13 years old (k remains 0.55 for adolescent females greater than 13 years old); height is measured in cm; serum creatinine is measured in mg/dL.

Renal function, blood pressure, cholesterol, and glucose results and their respective changes from baseline will be summarized by visit for subjects in the PP1, PP2 and the ITT samples by clinical phenotype.

Spaghetti plots for post-screening visits will be created for renal function measurements, blood pressure, cholesterol, and glucose.

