## **3. STUDY DESIGN**

### **3.1 DESCRIPTION**

This is a prospective multicenter, open-label, single-arm trial in which 20 pediatric recipients of parental living-donor liver allografts will be gradually withdrawn from immunosuppression with the goal of complete withdrawal. Patients on stable immunosuppression regimens with good organ

function and no evidence of acute or chronic rejection or other forms of allograft dysfunction will be enrolled. Participants will undergo gradual withdrawal of immunosuppression and will be followed for a minimum of 8 years after completion of withdrawal. Immunologic and genetic profiles will be collected at multiple time points and compared between tolerant and nontolerant individuals.

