## **3.4 RATIONALE FOR SELECTION OF STUDY POPULATION**

The study population is defined in section 4.1. The proposed study aims to prospectively identify a cohort of stable patients who underwent parental living-donor liver transplantation when they were less than 18 years of age. This choice stems from the following:

- The concerning incidence of renal dysfunction, hypertension, and metabolic abnormalities related to long-term use of immunosuppressive medications in long-term (5–10 years) pediatric survivors of liver transplantation.
- The substantial potential benefit (physical, psychosocial, and financial) resulting from immunosuppressive withdrawal that participants can enjoy over a long lifetime.
- The availability of donor blood and recipient blood and tissue for mechanistic testing.
- The minimal maintenance immunosuppression currently utilized in these patients (a single agent) may increase the likelihood of successful withdrawal.

Patients for whom the indication for transplantation was hepatitis B, hepatitis C, autoimmune hepatitis, or primary sclerosing cholangitis are excluded because these diseases may recur after transplantation and their posttransplant course may be affected by withdrawal or intensification of immunosuppression as necessitated by a precipitated episode of rejection.

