### 3.6 PACE OF ENROLLMENT AND STUDY DURATION

Enrollment is defined as starting on the day that immunosuppression withdrawal is initiated. Enrollment is planned for 2 years and will be limited to a maximum of two participants every 4 weeks. Maximum patient participation is up to 11 years; therefore, the total study duration is projected to be a maximum of 13 years.

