### 6.2 GENERAL ASSESSMENTS

These general assessments will be performed (see Appendices 1–4):

- Informed consent. Written informed consent and subject assent (if applicable) will be obtained before performing any study assessments or procedures.
- Demographic history. A history will be taken to obtain the participant's date of birth, sex, race, and ethnicity.
- General medical history. A history will be taken to document any present or past diseases, any past or planned medical/surgical procedures, and information on the condition under study. Additionally, the most recent results of any previous testing of ALT or alkaline phosphatase and GGT will be documented.
- Liver transplant specific medical history. Rejection episodes, history of any cancer, CMV, infectious episodes, medication change histories, indication for liver transplantation, and results from any liver biopsy performed less than 1 year before screening. (If results for that period are not available, results of the most recent liver biopsy before screening will be collected).

- Physical examination.
- Vital signs. Temperature, blood pressure, pulse, respiration, weight, and height will be recorded.
- Review of inclusion and exclusion criteria.
- PPD skin test. A purified protein derivative (PPD) test to assess infection with tuberculosis will be performed at screening. Results of a prior test performed within 1 year prior to screening will be accepted in lieu of the test at screening and will be recorded on the case report forms (CRFs)
- Telephone consultation. Telephone consultations will be performed as scheduled to assess adverse events, changes in concomitant medications, and compliance with study therapy and laboratory assessments.
- Adverse events. Participants will be assessed for adverse events at all site visits. All adverse events will be recorded on the CRFs.
- Concomitant medications. All reported concomitant medications will be recorded on the CRFs.

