#### **9.2.2 Analysis of Secondary Endpoints**

##### **9.2.2.1 Safety of Immunosuppression Withdrawal**

The following endpoints will be analyzed using the PP and ITT samples:

- The proportion of participants who have graft loss or who die after initiation of immunosuppression withdrawal will be descriptively summarized with a two-sided, 95% CI.
- Median time from initiation of immunosuppression withdrawal to first episode of acute rejection or to first diagnosis of chronic rejection, with a corresponding two-sided 95% CI, will be estimated using the Kaplan-Meier method.
- Distribution of severity among rejection episodes and the incidence of adverse events will be descriptively summarized using frequency tables with enumerations and percentages.
- Descriptive statistics (mean, standard deviation, mean change from baseline) for renal function, blood pressure, cholesterol level, and glucose control over time will be presented.

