10.6 Vital Signs, Physical Findings, and Other Observations Related to Safety

10.6.1 Vital Signs

Descriptive statistics of vital signs results and change from baseline of vital signs will be summarized for the PP1 and PP2 samples. Data listings will be provided for vital signs measurements. They will be sorted by subject, vital sign parameter and time of assessment. Data reported in English units will be converted to corresponding metric units (e.g., cm, kg, degrees C).

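### Blood pressure change is summarised with no age, sex or height standard, so in participants still growing it is biased upward and may hide a benefit of withdrawal or mimic harm

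*SAP*

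**What the plan says.** Change in blood pressure is listed among the secondary safety endpoints in Protocol 3.3.2.1 and SAP 3.2.2. Three places describe its analysis.

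- Protocol 9.2.2.1: "Descriptive statistics (mean, standard deviation, mean change from baseline) for renal function, blood pressure, cholesterol level, and glucose control over time will be presented".
- SAP 10.4.5: "Renal function, blood pressure, cholesterol, and glucose results and their respective changes from baseline will be summarized by visit", by clinical phenotype (tolerant or not), with spaghetti plots.
- SAP 10.6.1: "Descriptive statistics of vital signs results and change from baseline of vital signs will be summarized for the PP1 and PP2 samples". The only conversion named there is from English to metric units.

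Neither document names a blood pressure percentile, z-score, pediatric reference or hypertension category. That the summary will be in mmHg is inferred from this silence; no other scale is mentioned.

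The data for a standardised scale are already collected. Protocol 6.2 takes date of birth and sex, and for vital signs states "Temperature, blood pressure, pulse, respiration, weight, and height will be recorded".

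On the length of follow-up the documents differ. Protocol 3.1 has participants "followed for a minimum of 8 years after completion of withdrawal", and Protocol 3.6 adds "Maximum patient participation is up to 11 years; therefore, the total study duration is projected to be a maximum of 13 years". SAP 3.4 has them "followed for a minimum of 4 years after completion of immunosuppression withdrawal", and the SAP's schedules stop at the end of low-intensity follow-up.

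**The concern.** Eligibility requires transplantation before age 18 and at least 4 years earlier, so a child can enter at about 4. If blood pressure rises with growth, change from baseline adds normal growth to any effect of stopping the drug. The trial has one arm and 20 participants, so no comparator subtracts the growth.

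Display by phenotype makes this harder to read. Participants who fail withdrawal have about 52 more weeks of follow-up and are then discharged (Protocol 5.3 and 6.6). Late visits therefore hold mainly tolerant participants. The growth-related rise accumulates in their column with no long-term non-tolerant column beside it.

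The endpoint also bears on why this population was chosen. Protocol 3.4 cites "The concerning incidence of renal dysfunction, hypertension, and metabolic abnormalities related to long-term use of immunosuppressive medications". A mean change that contains growth is a poor way to show whether withdrawal relieves hypertension.

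The SAP allows for body size or reference values elsewhere. In SAP 10.4.5 itself, GFR uses height, an age- and sex-dependent constant and scaling to 1.73 m². In SAP 10.5, laboratory values are flagged against reference ranges. Blood pressure gets neither.

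**Working it through.** **The plan's own duration.** Enrollment of 2 years plus participation of up to 11 years gives 2 + 11 = 13 years, as Protocol 3.6 states. The schedule fits this: up to 11 weeks of screening (9 + 2), 24 monthly visits that include the 12 high-intensity weeks, then 104 + 104 + 208 = 416 weeks. That is 11/52 + 2 + 416/52 = 10.2 years.

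**Follow-up after the last dose, for those who stay off the drug.**

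- Protocol 6.6: 12 + 104 + 104 + 208 = 428 weeks; 428/52 = 8.2 years.
- SAP schedules: 12 + 104 + 104 = 220 weeks; 220/52 = 4.2 years. I use the SAP's stated 4 years below.

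**When the non-tolerant column empties.** A participant who restarts the drug just short of one year is non-tolerant and leaves about 52 weeks later, that is, about 2 years after the last dose (plus any time for liver tests to improve). Later visits hold essentially tolerant participants only.

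**Size of the growth component.** The documents give no figure. Assumption: normal growth adds g = 0.5 to 2 mmHg systolic per year until age 18 and nothing after. With T years of follow-up:

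growth-only change = g × min(T, max(0, 18 − age at entry))

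| Age at entry | Growing years, T = 4 | Change (mmHg) | Growing years, T = 8.2 | Change (mmHg) |
|---|---|---|---|---|
| 4 or 8 | 4 | +2 to +8 | 8.2 | +4.1 to +16.4 |
| 12 | 4 | +2 to +8 | 6 | +3 to +12 |
| 16 | 2 | +1 to +4 | 2 | +1 to +4 |
| 18 or over | 0 | 0 | 0 | 0 |

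If g were 0, every entry would be 0. A correctly standardised z-score has an expected growth-only change of 0. These horizons start at the last dose; a baseline before the taper lengthens the growing time. Over 10 years a child aged 4 or 8 would gain 5 to 20 mmHg. I rest the point on the shorter horizons.

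**Set against sampling noise.** The documents give no SD. Assume an SD of change of 8 to 12 mmHg. The 95% half-width for a mean change is t(0.975, n − 1) × SD/√n. For the two success counts used as examples in Protocol 9.3:

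- n = 9: 2.306 × 8/3 = 6.1 to 2.306 × 12/3 = 9.2 mmHg.
- n = 4: 3.182 × 8/2 = 12.7 to 3.182 × 12/2 = 19.1 mmHg.

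In a young cohort followed for 8.2 years, the growth component could match or exceed the noise with 9 tolerant participants. With 4, it would do so only near the top of the assumed range. In participants enrolled at 16 or older it is below the noise in both cases.

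**The case against.** The strongest reply is that the effect may be small in the cohort actually enrolled. Age is capped at transplantation, not at entry, and Protocol 3.2 has a consent band for participants aged 18 or over. The age mix is not given. This stands: a reader might infer that growth is bound to look like worsening blood pressure, but the documents support only an upward bias in those still growing. If withdrawal lowers blood pressure, the same bias would hide the benefit rather than show harm.

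The horizon is also open to challenge. The analysis criticised is the SAP's, and the SAP covers about 4 years, not 8 or 11. In the plan's own examples (9 or 4 successes of 20), 11 to 16 participants are not successes and may contribute no long-term change. Both facts limit the size. The second is also why the bias gathers in one column.

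A reader might further infer that growth outweighs any plausible effect of stopping the drug. The documents give no effect of withdrawal in mmHg, so that comparison cannot be made.

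Nor does standardising replace a control arm. Concomitant medication is unrestricted (Protocol 5.4), so antihypertensives can change, and participants who fail may receive corticosteroids (Protocol 5.5.3.3). Both would still affect a z-score.

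Finally, the analysis is descriptive, and other displays exist: spaghetti plots, vital-sign listings, adverse event tables, medication tables, and age at enrollment by phenotype. New clinical hypertension would not depend on the mean change alone to be noticed. These displays help a careful reader, but none takes growth out of the change from baseline.

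**Conclusion.** The point holds in a limited form. Neither document sets an age, sex or height standard for blood pressure. Change from baseline is therefore biased upward in participants still growing, mainly in the tolerant column at late visits. For a child aged 4 to 8 at entry, growth adds about 2 to 8 mmHg over the SAP's roughly 4 years and 4 to 16 mmHg over the protocol's 8.2 years. It adds 1 to 4 mmHg for someone enrolled at 16, and nothing in adults. All these figures rest on the assumed 0.5 to 2 mmHg systolic per year; no diastolic figure is offered. The overall bias depends on the unknown age mix.

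Only one component of a descriptive secondary safety endpoint is affected. The primary endpoint, sample size and stopping rules are not. The change is worth making because it is cheap and uses data already collected. The 4-year and 8-year follow-up statements also need reconciling, but the bias arises under either.

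**What to change.** Amend SAP 10.4.5, and refer to it from 10.6.1, as follows.

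- For participants under 18 at baseline, add change from baseline in systolic and diastolic z-score, standardised for age, sex and height, by visit. Name one pediatric reference in advance. Make this the main blood pressure summary for them.
- Compute change in z-score only at visits before age 18.
- For participants who are adults at baseline, and for visits after a participant turns 18, present raw mmHg separately. Do not mix scales within one change score: a z-score at baseline and mmHg at follow-up leave the change undefined.
- At each visit, show the proportion above the reference hypertension threshold for the participant's age. This can be followed across age 18.
- Keep raw values in tables and listings, with a note that raw change from a childhood baseline includes growth.

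The cost is a reference table and a little programming; no new data are needed. The downside is fewer participants in the z-score summary at late visits. Anyone older than 18 − 8.2 = 9.8 years at the last dose turns 18 before the protocol's follow-up ends; for the SAP's schedules the corresponding age is 18 − 4.2 = 13.8 years. Report the number contributing at each visit.
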